5.5 STRATEGIES FOR RECRUITMENT AND RETENTION

As indicated in the proposal, human subjects will be recruited for in-depth interviews (N=30) and surveys (N=50), in Aim 1 to understand preferred language, cultural beliefs, access to health care; healthcare engagement, knowledge of breast cancer screening guidelines and predictors of screening behavior. Recruitment will take place within African immigrant communities in New York City.

After incorporating the Aim 1 findings to our existing breast cancer educational program, 64 (n = 32 for English and n = 32 for French speaking) eligible African-born women will be recruited to pilot test the adapted educational program. Participants will be recruited from African immigrant communities in New York City.

Aim 1: Participants will be recruited from the community with the help of our community partner – African Services Committee. Our community partners will help us with our recruitment efforts by advertising the study within their organizations and at events and meetings they may hold for their consumers. Participants will be compensated \$30 to a local store for participating in the research study. In addition, we will promote our study on social media (e.g. WhatsApp groups, Facebook pages) using flyers and video advertisements adapted for online sharing.

Aim 2: Experienced outreach coordinators, assisted by our community partners, will recruit local community, faith-based, and other social organizations to host breast cancer educational programs as we

Based on "NIH Protocol Template for Behavioral and Social Sciences Research"

15

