6.1.2 ADMINISTRATION AND/OR DOSING

For Aim 1 of the study, interested individuals will be invited to perform the study activities in a single session, in which they will express informed consent, provide demographic data and complete an in-depth interview or an interviewer-administered survey. Once consented, participants may also complete the demographic questionnaire and/or the interview or survey on another time and/or day of their choice, if so they prefer (i.e., because they feel fatigued; if they have limited continuous availability of time).

For Aim 2 of the study, research staff will focus on sites that include African-born immigrant women 38 years of age and older. A program will be scheduled by the coordinator and individuals at the community sites will be approached to participate in a breast cancer educational program. Some programs will also be held virtually. We will conduct a total of eight programs in English (N=4) and French (N=4). We will recruit a total of 64 eligible women at each program. When recruiting program sites, the Research Assistant will emphasize the language in which the program will be conducted.

The administration of the intervention – including frequency, schedule, setting, and required personnel – will be determined using the input of individuals taking part in Aim 1 of the study.

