9.2 SAMPLE SIZE DETERMINATION

We estimate that our sample size of 64 participants will generate a +/- 12% margin of error at a 95% confidence level.

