9.3 POPULATIONS FOR ANALYSES

Per-Protocol Analysis Dataset

Based on "NIH Protocol Template for Behavioral and Social Sciences Research"

Descriptive statistics will provide summary information about the feasibility of recruitment, acceptability and cultural sensitivity of the program and satisfaction with the program. An arbitrary cutoff value of 80% acceptance will determine the interventions' feasibility for the study. Some parameters include the proportion of eligible participants who are enrolled, agree, and disagree with the acceptability and cultural relevance of the program. Thus, if at least 80% of the participants exceed the previous parameters, the adapted program will be determined to be feasible and acceptable. To determine program efficacy and sample size estimates for a future intervention, we will use a repeated measures ANOVA to analyze differences in the primary outcomes: screening intentions and HBM constructs (e.g., self-efficacy and perceived risk) immediately before viewing the educational program and immediately after viewing the program. We will conduct univariate and bivariate analyses of the data to provide descriptive summaries of the data, including demographics and responses to primary outcome measures.

We expect only minor amounts of missing data from the surveys and feasibility questionnaires. However, we will examine any patterns of missing data and if needed, consider using missing data imputation methods.

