9.4 STATISTICAL ANALYSES

9.4.1 GENERAL APPROACH

For Aim 1 demographic characteristics of the participants will be reported. Data from the quantitative surveys will be analyzed to identify predictors of non-adherence to breast cancer screening. We will conduct univariate and bivariate analyses of the data to provide descriptive summaries of the data, including demographics and responses to primary outcome measures. Data from the audio-recorded in-depth interviews will be transcribed verbatim from audio recordings (using a transcription service). Analyses of the qualitative data will be conducted using the PEN-3 model, which is a method of analyzing data focusing on social processes and actions. The goal of our qualitative research is to identify the unique barriers and facilitators African immigrant women encounter with breast cancer screening. In line with this approach, the coding steps of open coding, axial coding, and selective coding will be used to identify categories and develop properties. Memoing will be conducted throughout the process. A constant comparative method will be used to generate theoretical categories and refine concepts.

For Aim 2, we will conduct univariate and bivariate analyses of the data to provide descriptive summaries of the data, including demographics and responses to primary outcome measures. Independent samples t tests will be used to compare changes in the primary outcomes measures pre-education and post-education. Using a pre-post test design, we will analyze differences in the three primary outcomes: screening intentions, self-efficacy and perceived risk immediately before viewing the educational program and immediately after viewing the program.

To determine program efficacy and sample size estimates for a future intervention, a generalized linear modelling approach will be used with logistic regression. We will use a repeated measures ANOVA to analyze differences in the primary outcomes: screening intentions and HBM constructs (e.g., self-efficacy and perceived risk) immediately before viewing the educational program and immediately after viewing the program. We will conduct univariate and bivariate analyses of the data to provide descriptive summaries of the data, including demographics and responses to primary outcome measures.

Based on "NIH Protocol Template for Behavioral and Social Sciences Research"

23

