10.1 REGULATORY, ETHICAL, AND STUDY OVERSIGHT CONSIDERATIONS

10.1.1 INFORMED CONSENT PROCESS

10.1.1.1 CONSENT/ASSENT AND OTHER INFORMATIONAL DOCUMENTS PROVIDED TO PARTICIPANTS

For Aim 1, consent forms describing in detail the study intervention, study procedures, and risks will be given to the participant and written documentation of informed consent will be completed prior to starting the study intervention. The following consent materials are submitted with this protocol:

- In-depth interview consent form (English and French)
- Survey consent form (English and French)

For Aim 2, we have requested a waiver of written consent due to the extremely low risk of this research as no PHI will be collected from participants. We are unable to consent participants prior to the program because we will not have their contact information (as we are not collecting any PHI) – participants will be recruited and invited to the programs by community partners. We anticipate having up to 10 participants in each program and we will have limited staff available to consent participants. Based on past experience, doing a full consent process with each individual participant is not feasible (for example, consenting procedures for Aim 1 have taken up to 45 minutes for some participants). Since participants will be part of group sessions, the time and study personnel needed to individually consent each participant would become an undue burden for the participants. Each individual will be informed of study procedures and will give informed consent through reviewing a Research Information Sheet and verbally confirming their willingness to participate before engaging in the research. This also allows participants to become anonymous since we are not collecting their names or signatures, and privacy is a demonstrated concern for this population. Individuals will review, either via RedCap or hard copy, the

Based on "NIH Protocol Template for Behavioral and Social Sciences Research"

25

Research Information Sheet that will provide details about the research study. If individuals agree to participate in the study, they will confirm their eligibility for the study. The following materials are submitted with this protocol:

- Pilot intervention research information material based on waiver of written documentation of consent: Research Information Sheet (English and French)

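### The repeated measures ANOVA for Aim 2 treats 64 women taught in eight group programs as independent; if change is correlated within program, its standard errors are too small.

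*Combined protocol and SAP*

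**What the plan says.** Aim 2 is a one-group pre-post pilot. Section 6.1.2 sets the delivery: "We will conduct a total of eight programs in English (N=4) and French (N=4". Section 5.5 sets the total: "64 (n = 32 for English and n = 32 for French speaking) eligible African-born women will be recruited". Section 10.1.1.1 gives the expected group size, "We anticipate having up to 10 participants in each program", and argues for a consent waiver partly on the ground that delivery is collective: "Since participants will be part of group sessions". Under section 6.1.1 each program consists of the pre-program survey, a narrative presentation, an interactive discussion and then the post-program survey.

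Section 9.4.1 names three methods for Aim 2: independent samples t tests, a generalized linear model with logistic regression, and the ANOVA: "We will use a repeated measures ANOVA to analyze differences in the primary outcomes". Section 9.3 repeats the ANOVA and gives its purpose: "To determine program efficacy and sample size estimates for a future intervention, we will use a repeated measures ANOVA". The outcomes listed with it are screening intention and HBM constructs such as self-efficacy and perceived risk.

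None of these methods has a program term, random effect, clustered variance or ICC, and no other section supplies one. Section 6.1.1 links the pre and post surveys by participant study ID only. A program summary records site and attendance, but the plan does not tie it to the participant records.

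**The concern.** The program is delivered to a group, and what happens in the room comes between the two surveys. A lively discussion, or one persuasive question, can move everyone present in the same direction. The women's changes would then not be independent, and a model whose only unit is the woman credits the data with more information than they hold.

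Two stated uses are exposed. The first is the efficacy comparison: with correlated change, the ANOVA gives intervals that are too narrow and p-values that are too small. The second is planning. These analyses are meant to supply sample size estimates for a future intervention. If that intervention is again delivered in groups, between-program variance is a planning input, and the plan never estimates it. Because the records are anonymous, a program number that is not stored at collection may not be recoverable later.

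**Working it through.** **Inputs.** From the documents: 64 women (5.1, 5.5, 10.1.1.2); 8 programs, four per language (6.1.2); up to 10 women per program (10.1.1.1). The average is 64 / 8 = 8 per program. Assumed: equal program sizes; a continuous change score; a nominal 5% two-sided test, because no alpha is stated for Aim 2 (the 0.15 criterion in 9.4.2 is given for Aim 1); and an ICC of change from 0.01 to 0.10, because the documents give none.

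**The plan's own figure.** Section 9.2 says: "We estimate that our sample size of 64 participants will generate a +/- 12% margin of error at a 95% confidence level". With p = 0.5 and n = 64, 1.96 × √(0.25/64) = 12.25%, so the figure reproduces with 64 independent observations, that is, a design effect of 1. It is a precision statement for one proportion and is not the target here.

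**Reduction of the ANOVA.** With two time points and one group, repeated measures ANOVA is the paired t test on change: 64 change scores, 63 df.

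**Formulas.**
- Design effect: DE = 1 + (m − 1) × ICC, with m = 8.
- True SE / naive SE = √DE.
- Effective n = 64 / DE.
- Approximate type I error of the naive test: 2 × [1 − Φ(1.96/√DE)].
- Interval width on 7 df relative to the plan: (t₇/t₆₃) × √DE = (2.365/1.998) × √DE = 1.183 × √DE.

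| ICC of change | DE | SE ratio | Effective n | Type I error, approximation | Type I error, simulation | Relative interval width, 7 df |
|---|---|---|---|---|---|---|
| 0.01 | 1.07 | 1.03 | 59.8 | 5.8% | about 5.8% | 1.22 |
| 0.02 | 1.14 | 1.07 | 56.1 | 6.6% | about 6.6% | 1.26 |
| 0.05 | 1.35 | 1.16 | 47.4 | 9.2% | about 9.0% | 1.37 |
| 0.10 | 1.70 | 1.30 | 37.6 | 13.3% | about 13.2% | 1.54 |

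The simulation draws change as a program effect plus individual error, in eight programs of 8. Repeat runs differ by a few tenths of a percentage point. A t test on the eight program means (7 df) stays at about 5% throughout.

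**The other planned test.** The independent samples t test ignores pairing as well as program. With pre-post correlation ρ, its SE divided by the true SE is 1/√[(1 − ρ) × DE]. At an assumed ρ of 0.5 this is 1.37 / 1.22 / 1.09 for ICC 0.01 / 0.05 / 0.10, which is too large. At ρ = 0.3 and ICC 0.10 it is 0.92, which is too small. The direction is therefore not fixed.

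**How well eight programs estimate an ICC.** In simulation with a true ICC of 0.05, 95% of the estimates lay between −0.09 and 0.24.

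**The case against.** The strongest reply is that little turns on these tests. Section 4.1 confines the study to the adaptation stages before an effectiveness trial, and the stated decision rule in 9.1 and 9.3 is a descriptive 80% cutoff. That is fair and limits the consequence. It does not remove the point, because 9.3 and 9.4.1 still assign these models to efficacy and to sizing future work.

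The second reply is that the size is unknown. Stable traits shared by women from the same community largely cancel in a change score taken within one 90-minute program, so a common background is weak evidence for correlated change. At an ICC of 0.01 the effect is small. Both observations stand. What remains is the shared presentation and discussion between the two surveys.

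Four stronger readings are tempting, and the documents do not support them:

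- *Standard errors are too small for both primary endpoints.* The synopsis makes intention and mammogram location primary, but 9.3 and 9.4.1 assign location to no model, so nothing can be said about its standard error.
- *Every planned test is anticonservative.* The independent samples t test can overstate the standard error, as shown above.
- *Each program has one speaker and one host organisation.* No section says this. Section 2.2 describes a survivor with lay volunteers, section 6.1.1 refers to trained staff, and some programs are virtual.
- *The tabulated error rates apply to the intention item itself.* Section 3 gives that item five response options and defines no coding for it. The simulation used a continuous score.

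**Conclusion.** The point holds for the repeated measures ANOVA of screening intention and the HBM scales. Any positive within-program correlation of change makes its standard errors too small: by a factor of 1.03 at an ICC of 0.01, rising to 1.30 at 0.10, with type I error of about 5.8% rising to 13.2%. The direction follows from the design. The size depends on an assumed ICC, eight programs of 8, a continuous change score and a nominal 5% test. The logistic model also lacks a program term, but no size is claimed for it because its outcome coding is not given.

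This is worth correcting because it is cheap and bears on the pilot's stated planning purpose. It does not undermine the feasibility result.

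One inconsistency affects the layout. Section 6.1.2 also says "We will recruit a total of 64 eligible women at each program", which over eight programs would be 8 × 64 = 512 women. That conflicts with 64 in total (5.1, 5.5, 10.1.1.2) and with up to 10 per program (10.1.1.1). The calculation takes 64 as the total, and the sections must be reconciled.

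**What to change.** 1. Store the program number (1 to 8) with each anonymous study ID at collection. It names no one.
2. In 9.3 and 9.4.1, replace the unclustered pre-post tests with an analysis of within-woman change that accounts for program. Suitable choices are a mixed model with a random program effect and small-sample degrees of freedom, or a t interval on the program mean changes.
3. Include language as a fixed factor. It is nested in program, four programs each, and if left out, any language difference would be counted as between-program variance.
4. Treat any binary endpoint the same way once its yes/no coding is defined, and state which analysis covers mammogram location.
5. Report the between-program variance or ICC of each outcome descriptively with its interval, and say that eight programs estimate it imprecisely.
6. Reconcile the session-size sentence in 6.1.2 with the total in 5.1, 5.5 and 10.1.1.2 and the group size in 10.1.1.1.

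**Cost.** One extra field and revised wording. Intervals become about 20% to 55% wider over this ICC range on 7 df. Of that, 18% comes from the change in degrees of freedom alone (2.365/1.998 = 1.18). Fitting language to the program means takes one more degree of freedom (8 − 2 = 6), so intervals widen slightly further unless language explains some of the variation between programs.

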9.4.2 ANALYSIS OF THE ENDPOINT(S)

Quantitative Data Analysis: As the assessment will be administered as an interview, we do not anticipate much missing data. As needed, missing data will be imputed and then be used to estimate the parameter values for each of scales. We estimate that our sample size of 64 participants will generate a +/- 12% margin of error at a 95% confidence level. The primary outcomes are screening status (up-to-date with for mammography screening) and HBM constructs. As screening status is dichotomous, a logistic regression analysis will be conducted using socio-demographics and HBM constructs (e.g., self-efficacy, perceived risk, perceived benefits) as explanatory variables. Since Aim 1 is designed to provide information to inform the adaptation of the subsequent intervention and education, we shall adopt a less conservative criterion for statistical significance using a *p*-value equal to or less than 0.15.

Qualitative Data Analysis. The PEN-3 model²⁵ will guide the interpretation and analysis of the in-depth interviews. Using this model as a framework, the analysis approach will identify the unique barriers and facilitators related to African-born immigrants' health care engagement. Transcripts will be reviewed using a qualitative data management software.⁵⁰ Analysis will use a content analysis approach – which includes examining transcripts for salient categories of information supported by the text (e.g., barriers and facilitators to uptake of cancer screening in African immigrants). Themes that are extensively discussed by participants will be coded. Using a constant comparative approach, categories will be saturated until new information is no longer added. The research team will meet prior to conducting analysis to define coding labels and definitions. Potential labels and definitions will be drawn from identified barriers and facilitators for other preventive cancer screening exams (e.g., pap test, colonoscopy). All transcripts (including those translated from French to English) will be independently coded by PI [name] and research coordinators using the same framework to ensure consistency. They will meet multiple times to discuss the coding strategy for the first half of the interviews and discuss and resolve any coding discrepancies prior to coding of the remaining interviews, and again to resolve any remaining discrepancies by consensus. When there is disagreement on coding labels, the research team will meet to discuss reasons for disagreement and modify coding labels appropriately. Analyses will also examine subgroup differences (i.e., country of origin), age, and language. Our proposed sample size of 30 in-depth interview participants will be stratified by language and we anticipate achieving saturation with these sample sizes. If saturation is not achieved with the 30 participants, we will recruit more participants with collaborators and community partners.

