5 STUDY POPULATION

5.1 INCLUSION CRITERIA

- Eligibility criteria for Aim 1 include (n=80):
 - i. Eligible individuals for Aim 1 in-depth interviews with leaders (N=10) will be:
 - 1) 18 years or older;
 - 2) stakeholder/gatekeeper in the African immigrant community;
 - 3) speak English or French.
 - ii. Eligible individuals (n=70) for Aim 1 In-depth Interviews and Quantitative Surveys will be:
 - 1) women who are 40 years or older;
 - 2) have been born in Africa;
 - 3) speak English or French.

Based on "NIH Protocol Template for Behavioral and Social Sciences Research"

14

- Eligibility criteria for Aim 2 include (n=64):
 - 1) women who are 38 years or older;
 - 2) have been born in Africa;
 - 3) speak English or French.
 - 4) Smartphone or computer with zoom (for virtual programs)

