10.1.1.2 CONSENT PROCEDURES AND DOCUMENTATION

Aim 1: Participants will be recruited from African immigrant communities in New York City. We have a well-established collaborative relationship with gatekeepers in the African immigrant community and have successfully recruited African-born persons into prior studies and therefore anticipate successful recruitment for this proposed research. Participants will be recruited for in-depth interviews and surveys through IRB approved flyers at community sites and via social media platforms. Advertisements for recruitment will be in English and French and identical for both languages. A bilingual Research Assistant (English and French) will administer the in-depth interviews (n=30), which will take 60 minutes to complete and administer the surveys (N=50) which will take about 20 minutes to complete.

Aims 2: Similar to recruitment for Aim 1, participant recruitment for Aim 2 will occur in African immigrant communities in New York City. After refining the education programs using the findings from Aim 1, 64 new participants (n=32 per language) will view the culturally-adapted education breast cancer screening program, after reviewing the Research Information Sheet and confirming their eligibility.

On the day of the program, participants will review, either via RedCap or with a hard copy, the Research Information Sheet that will provide details about the research study.

In person programs:

After participants arrive at the program, but before study procedures begin, study team members will distribute to each participant hard copies of the Research Information sheet and/or online versions via RedCap link that participants can access on their own or study team provided devices. Study team members will review the Research Information Sheet with each participant, privately and one on one, and answer any questions. Participants will also have the ability to read through the Research Information Sheet. Study team members will tell participants that participation is voluntary and will not impact their ability to seek medical care at Mount Sinai, discuss the expectations of participation (participating in an educational program, completing surveys, giving feedback on the educational program), discuss compensation (\$60 giftcard), communicate that no PHI will be collected (all information will be anonymous), and explain risks and benefits.

Virtual programs:

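### Section 9.4.2 gives the Aim 1 survey the Aim 2 sample of 64 and its ±12% margin, although that survey has 50 participants (±13.9%); Section 6.1.2 misstates the Aim 2 total, and Section 9.2 should say what the 12% measures

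*Combined protocol and SAP*

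**What the plan says.** The whole of Section 9.2 is one sentence on precision, repeated word for word in the quantitative part of Section 9.4.2: "We estimate that our sample size of 64 participants will generate a +/- 12% margin of error at a 95% confidence level". Neither place names the quantity estimated, the assumed proportion or an independence assumption.

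In Section 9.4.2 the sentence follows "As the assessment will be administered as an interview, we do not anticipate much missing data". The paragraph then names up-to-date mammography status and Health Belief Model constructs as outcomes, plans a logistic regression for screening status, and adopts a threshold of p ≤ 0.15. Its reason for that threshold begins "Since Aim 1 is designed to provide information to inform the adaptation of the subsequent intervention and education".

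The samples are set out elsewhere:

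- Aim 1, Section 5.5: "human subjects will be recruited for in-depth interviews (N=30) and surveys (N=50), in Aim 1". Section 10.1.1.2 confirms the survey count: "administer the surveys (N=50) which will take about 20 minutes to complete".
- Aim 2, Section 10.1.1.2: "64 new participants (n=32 per language) will view the culturally-adapted education breast cancer screening program". Sections 5.1 and 5.5 give the same total.

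Section 6.1.2 plans eight Aim 2 programs, four in each language, and then puts the recruitment of 64 women at every program. Section 10.1.1.1 expects no more than ten women per program.

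**The concern.** A precision statement is useful only if it belongs to the sample it is attached to. In Section 9.4.2 a reader would conclude that Aim 1 survey percentages rest on 64 women and are known to within 12 points. The survey has 50, so the stated precision is too favourable.

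Section 6.1.2 raises a related problem. It is where staff would look to see how the programs are run, and read literally it sets an Aim 2 enrolment eight times the total given elsewhere.

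In Section 9.2 the sample is the right one, but the sentence does not say what the margin applies to. The Aim 2 primary endpoint is a change from before to after the program (Synopsis; Section 3). A reader could take the 12% as the precision of that change, which the sentence does not establish.

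**Working it through.** **1. Reproduce the plan's figure.** The half-width of a 95% interval for one proportion from independent observations is 1.96 × √(p(1 − p)/n). The documents give no p, so I take the worst case, p = 0.5. For n = 64: 1.96 × √(0.25/64) = 1.96 × 0.0625 = 12.25%, which rounds to the stated 12%.

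**2. Which aim does the Section 9.4.2 paragraph describe?** Four features point to Aim 1:

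- The significance threshold is justified by reference to Aim 1.
- The assessment is interviewer-administered. Section 6.1.2 describes the Aim 1 survey that way, whereas Section 6.1.1 has the Aim 2 surveys collected mainly through RedCap.
- The outcome is current screening status. Section 9.4.1 places this analysis under Aim 1: "Data from the quantitative surveys will be analyzed to identify predictors of non-adherence to breast cancer screening". The Aim 2 primary endpoints are screening intention and knowing where to get a mammogram.
- The next paragraph of Section 9.4.2 covers the Aim 1 interviews.

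**3. Could 64 be an Aim 1 count?** No. The Aim 1 counts are 10 leaders, 70 women, 30 interviews, 50 surveys and 80 overall. Section 6.1.2 has each Aim 1 participant complete an interview or a survey, so the survey count is 50.

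**4. Margin for the right sample.** For n = 50: 1.96 × √(0.25/50) = 13.86%. The difference is 13.86 − 12.25 = 1.61 points. At 56%, the share ever screened in Section 2.2 (which is not the same as up to date), the margin is 1.96 × √(0.56 × 0.44/50) = 13.76%, so the choice of p hardly matters here.

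**5. Section 6.1.2.** Read literally, 8 × 64 = 512 women. A total of 64 is 64/8 = 8 per program. A maximum of ten per program allows 8 × 10 = 80. Only the total of 64 fits the other sections.

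**6. What the 12% in Section 9.2 covers.** For a paired yes/no item with no net change, the margin is 1.96 × √(ψ/64), where ψ is the share of women who switch answer. The documents give no ψ. For assumed values of 10%, 25%, 40% and 50% it is 7.7%, 12.2%, 15.5% and 17.3%. The stated 12% therefore matches the change only if about a quarter switch, which would be coincidence.

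**7. Clustering, as illustration only.** The documents give no intraclass correlation (ICC). With 8 women per program the design effect is 1 + 7 × ICC, and the margin at p = 0.5 is 12.25% × √(design effect):

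| Assumed ICC | Design effect | Margin |
|---|---|---|
| 0.01 | 1.07 | 12.7% |
| 0.05 | 1.35 | 14.2% |
| 0.10 | 1.70 | 16.0% |

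**The case against.** The strongest reply is that nothing has been miscalculated. The sentence is correct for the 64 it names, and Section 9.4.2 never says outright that the survey has 64 participants. On this view it is a stray duplicate of Section 9.2. The survey size is clear in two other sections, no Aim 1 test or decision uses the 12%, and the regression does not depend on it. All of this stands, and it limits the consequence. It does not remove the error: the sentence still gives the wrong sample in the paragraph where it appears.

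For Section 6.1.2 the reply is that it is a drafting slip. That is very likely, since the same sentence uses the word total and three other sections agree on 64. A reader might infer that 512 women are planned; the documents as a whole do not support that. The contradiction still needs an edit.

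A reader might also go further on Section 9.2 and conclude that the 12% is wrong because women attend in groups. The documents do not support this either. The figure is right for a single proportion from independent women, and a single proportion suits the acceptability percentages. Near 80% the margin under independence is 1.96 × √(0.8 × 0.2/64) = 9.8%, so 12% is cautious there. Every clustered figure above rests on an assumed ICC.

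Nor do the documents show that program membership will be lost. Section 6.1.1 describes no program identifier on the surveys, but it does not say whether study IDs or survey links can be traced to a program.

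**Conclusion.** Two statements are wrong as written. Section 9.4.2 attaches the Aim 2 sample to the Aim 1 survey; for 50 participants the worst-case margin is ±13.9%, 1.6 points wider than for 64. This rests on the normal approximation, p = 0.5 and independent respondents, and it concerns descriptive percentages only. Section 6.1.2 conflicts with Sections 5.1, 5.5 and 10.1.1.2 on the Aim 2 total, and with Section 10.1.1.1 on program size.

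Section 9.2 is not wrong. It is incomplete, because it leaves the reader to guess what the margin measures; one added sentence is enough.

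A reader might infer that these points undermine the feasibility decision. They do not: the 80% rule in Sections 9.1 and 9.3 compares observed percentages with a cutoff and does not use the margin. None of the three points calls for more participants or a different design.

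**What to change.** - **Section 9.4.2:** delete the sentence, or replace it with a statement that 50 survey participants give a worst-case 95% margin of ±13.9% for a single proportion. One line.
- **Section 6.1.2:** reconcile the wording with 64 women in total across the eight programs, 32 per language. One line.
- **Section 9.2:** add one sentence saying that ±12% is the margin for a single proportion at 0.5 with independent responses, and is not offered as the precision of the pre-post change.
- **Optional:** record a bare program number on each survey, if the IRB privacy terms allow it, and report program-clustered intervals as a sensitivity analysis. The ICC of a within-woman change need not equal that of a percentage at one time point, so one assumed value should not be carried across both.

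The first three changes cost only wording, with a slightly less favourable stated precision for Aim 1. The optional step has real downsides. Intervals become wider. Eight programs give a very imprecise ICC: with SE = √(2(1 − ρ)²(1 + 7ρ)²/(8 × 7 × 7)), an ICC of ρ = 0.05 has a standard error of about 0.09. A program number also adds some re-identification risk in groups of about eight, in a study whose waiver of written consent relies partly on anonymity (Section 10.1.1.1).
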